### 10.7.2. Dolutegravir, Protein Binding and Hyperbilirubinemia

Dolutegravir is a well-tolerated potent ARV with minimal side effects. The drug is highly bound to plasma proteins and can displace bilirubin from albumin. DTG poses a theoretical risk of increased free bilirubin concentrations in the neonate at high DTG concentrations and in the presence of low serum albumin. However, DTG concentrations achieved in adults at approved DTG dosing are much lower than concentrations expected to result in the displacement of bilirubin from albumin (52).

An *in-vitro* experiment performed in the presence of low albumin concentrations has shown DTG to displace bilirubin from albumin to an equivalent extent as sulfisoxazole, raising concerns of increased free bilirubin and risk of bilirubin neurotoxicity. The clinical relevance of these experimental findings are however unclear as normal albumin concentrations (500-700 µmol/L) in adults and children typically exceeds DTG plasma concentrations by around 100-fold. The authors conducting these *in-vitro* studies conclude that unless the DTG concentrations are very high in a neonate, it is unlikely to have a significant impact on bilirubin to albumin binding because of the low DTG concentrations relative to the amount of albumin in the body (52).

To minimize the risk of bilirubin toxicity, we will exclude neonates born from mothers with known blood group incompatibility that can result in haemolytic disease of the newborn. We will not enroll neonates at high risk of bilirubin toxicity, which include preterm neonates, unwell neonates with a history of birth trauma, those with hypothermia, or suspected sepsis (53). Neonates with very high bilirubin values close to exchange, as defined by local guidelines (47), will also not be eligible for the study. Total and direct bilirubin will be drawn at baseline and monitored throughout the study. For safety purposes, a single dose of DTG will first be administered to older neonates (>2 weeks of age) in Cohort 1A, before moving to a single dose in younger neonates (<2 weeks of age) in Cohort 1B. Only if no safety concerns are observed will a multi-dose DTG strategy be considered, and neonates enrolled into Cohort 2.

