## 7.2. Exclusion Criteria

The presence of any of the following at entry, will exclude a subject from study enrolment:

- Less than 37 weeks gestational age at birth
- Known blood group incompatibilities which can result in hemolytic disease of the newborn (e.g., Rh-negative mother, presence of antibodies on neonatal red blood cells, etc.)
- Total bilirubin values approaching an exchange transfusion as defined by local guidelines (Section 18.2)
- Haemoglobin value of <13.0 g/dL
- Platelet count of less than 50,000 cells/mm^3)
- Decreased total white blood cell count (Grade 3 and above)
- Creatinine value more than 1.3 the upper limit of normal (ULN) for gestational age and postnatal age (Grade 2 and above)
- AST or ALT of more than 2.5 the ULN (Grade 2 and above)
- Any other current Grade  $\geq 3$  event on the DAIDS toxicity table
- Severe congenital abnormalities or critically ill neonates at discretion of the examining clinician
- Receiving medicine(s) that can impact DTG pharmacokinetics (Section 8.7)
- Participation in another clinical trial
- HIV-infected neonates

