### **13.6. Potential Benefits and Risks of the Research to the Subject**

The generic DTG 10 mg scored dispersible tablet from Viartis Ltd has received tentative approval from the U.S. FDA for use in infants and children 4 weeks and older and weighing at least 3 kg, and is currently under review with SAHPRA for regulatory approval in South Africa. Regulatory approval has not been requested for neonates due to lack of PK and safety data in this population. The PETITE-DTG study will generate this data for DTG in neonates, which will inform future ARV dosing and DTG use in neonates for HIV prevention and treatment.

We are proposing a study that requires the collection of personal and clinical data, as well as blood specimens, from neonates born to mothers living with HIV. Data will be entered into the clinical trial database by the site or CRFs may be scanned and emailed using secure encrypted systems to the data centre for data entry. All data will be de-identified and anonymised as to protect participant confidentiality. The PETITE-DTG study will comply with International General Data Protection Regulation (GDPR) and South African POPIA principles (Section 13.8). Most study procedures are routine medical procedures that are associated with minimal to no risk in participants. Blood collection may cause some discomfort and some bleeding or bruising may occur where the needle enters the skin. Well-trained and experienced study staff will perform the phlebotomy to minimize risk.

The potential risk of participation in this study is associated with the neonatal administration of DTG. Thus, all participants enrolled will be healthy HIV-exposed neonates born to mothers with HIV on a DTG-based ARV regimen. All neonates will be of term gestation and have a minimum birth weight of  $\geq 2000$  grams as no DTG data are available for preterm neonates.

In South Africa, women with HIV routinely receive an HIV-1 VL at delivery and their infants receives a minimum of 6 weeks of ARV postnatal prophylaxis, dependent on the risk of HIV acquisition in the infant. All HIV-exposed neonates start a prophylaxis regimen of NVP and ZDV at birth and continue this until the maternal VL result is available. If the maternal VL at delivery is  $\geq 1000$  copies/mL the infant is classified as 'high-risk' and continues both ARVs, else infants are deemed 'low'-risk and ZDV is stopped and NVP continued (1).

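### Section 10.7.2 says infants who are unwell with birth trauma, hypothermic or with suspected sepsis will not be enrolled, but the exclusion lists in Section 7.2 and the synopsis contain none of the three

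*Protocol*

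**What the plan says.** Section 10.7.2 discusses displacement of bilirubin from albumin by dolutegravir and then lists the measures meant to limit that risk. One is an enrolment commitment without qualification: "We will not enroll neonates at high risk of bilirubin toxicity, which include preterm neonates, unwell neonates with a history of birth trauma", followed by "those with hypothermia, or suspected sepsis". The paragraph also excludes infants whose mothers have a known blood-group incompatibility and infants whose bilirubin is close to the exchange level.

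The operative list is in Section 7.2, which opens: "The presence of any of the following at entry, will exclude a subject from study enrolment". It includes "Less than 37 weeks gestational age at birth" and "Known blood group incompatibilities which can result in hemolytic disease of the newborn", as well as total bilirubin approaching exchange. Its only items on general illness are "Severe congenital abnormalities or critically ill neonates at discretion of the examining clinician" and any other current DAIDS event of Grade 3 or higher. The synopsis gives the same criteria. Section 13.6 describes the population in general terms: "Thus, all participants enrolled will be healthy HIV-exposed neonates born to mothers with HIV on a DTG-based ARV regimen".

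**The concern.** Half of the risk groups in one paragraph were carried into the eligibility criteria and half were not. A safeguard promised in the safety section therefore has no matching criterion, and the two sections give different answers about the same infant.

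Three things are at stake.

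- **Who is dosed.** Cohort 1B enters at 3 days of life or less and Cohort 2 before 7 days. Section 10.7.1 places the bilirubin peak in term infants at about day 3. Cohort 2 infants then receive repeated doses until day 28.
- **Attribution.** The hold rules in Section 11.1 depend on whether an event is judged related to study drug. In Cohort 2, any related event leading to permanent discontinuation pauses accrual, and Section 10.8 requires permanent discontinuation at an exchange-level bilirubin. That judgement is harder in an infant who entered with one of these risk factors.
- **What counts as a deviation.** Section 12.2.6 plans an analysis of protocol deviations. Enrolling such an infant breaches Section 10.7.2 but no listed criterion in Section 7.2, so the protocol does not settle how to classify it.

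**Working it through.** No arithmetic applies. The check sets each risk group named in Section 10.7.2 against the exclusion criteria in Section 7.2 and the synopsis.

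| Risk group in Section 10.7.2 | Named in Section 7.2 and synopsis? |
|---|---|
| Blood-group incompatibility | Yes |
| Prematurity | Yes (below 37 weeks) |
| Bilirubin close to exchange | Yes |
| Unwell with a history of birth trauma | No |
| Hypothermia | No |
| Suspected sepsis | No |

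Three of six are carried over and three are not. The next step is whether other text covers the missing three.

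1. **Inclusion criteria (Section 7.1).** These cover HIV exposure, maternal treatment, birth weight, prophylaxis and age, plus maternal viral load in Stage 2. None requires the absence of the three conditions.
2. **The critically ill item (Section 7.2).** This sets a higher bar than suspected sepsis or hypothermia, and it is discretionary where Section 10.7.2 is absolute.
3. **The Grade 3 or higher item (Section 7.2).** This catches severe presentations only.
4. **The opening of Section 7.** It asks that all relevant conditions be considered and that eligibility questions go to the Principal Investigator before enrolment. It names none of the three and excludes nobody by itself.
5. **Screening (Section 9.1).** A medical history and clinical examination are taken, and Tables 6 to 8 include vital signs in the physical assessment. The conditions could therefore be noticed. The stated allocation condition is that bloods fall in the eligible range; this is necessary but not said to be sufficient, and no rule says what to do if one of the three is found.
6. **Section 13.6.** Calling participants healthy is descriptive text, not a criterion with a threshold.

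What remains is an infant with suspected sepsis or hypothermia, or unwell with birth trauma, who is not judged critically ill and has no event of Grade 3 or higher. That infant meets every listed criterion and is excluded by Section 10.7.2.

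**The case against.** The strongest reply is that Section 10.7.2 is itself protocol text, so enrolling such an infant would already contravene the protocol. The study has a single site, screening includes history and examination, and Section 7 tells the investigator to weigh all relevant conditions. The most direct measure of the hazard, bilirubin near exchange, is a listed exclusion, and bilirubin is monitored afterwards. A careful investigator may well decline these infants.

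Much of this stands. Section 7.2 is not silent about ill infants, and the sickest would be caught. But a general instruction and clinical judgement do not implement an unconditional commitment, and they cannot settle which section governs when the two disagree.

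Several stronger readings are tempting but unsupported.

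- A reader might infer that every infant with birth trauma was meant to be excluded. Section 10.7.2 says *unwell* infants with such a history, so a well infant is not clearly covered. Whether *unwell* also governs hypothermia and suspected sepsis is ambiguous. Even if it does, unwell is a lower bar than critically ill, and the mismatch remains.
- A reader might infer that the protocol regards dolutegravir as most dangerous in these infants. It says they are at high risk of bilirubin toxicity, but it does not rank the drug's hazard. It calls the displacement risk theoretical, its clinical relevance unclear, and a significant effect unlikely unless concentrations are very high.
- A reader might infer that sites will enrol on blood results alone. Section 9.1 does not say so.
- A reader might want the expected number of such infants among the 40. The protocol gives no frequency, so any figure would be invented.

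**Conclusion.** The contradiction holds. Section 10.7.2 claims an enrolment safeguard for six risk groups; Section 7.2 and the synopsis implement it for three. The gap is confined to infants with one of the other three conditions who fall below the critically ill and Grade 3 thresholds. Because Section 7.2 covers both stages, the gap exists in every cohort.

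This is more than missing detail, since two parts of the protocol give opposite answers on whether the same infant may be enrolled. It is not evidence that unsafe enrolment will occur, nor can its frequency be sized from the document. The conclusion rests on reading Section 7.2 as the list that decides exclusion, as its opening words say, and Section 10.7.2 as a commitment, as its wording says. It needs no assumption about how often the conditions arise.

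**What to change.** Reconcile the synopsis, Section 7.2 and Section 10.7.2 so that the eligibility lists and the stated safeguard agree. There are two ways to do this, and the choice is the sponsor's:

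- carry the three conditions into Section 7.2 and the synopsis as explicit exclusions at entry, keeping *unwell* for birth trauma and making clear whether it also applies to hypothermia and suspected sepsis; or
- if these exclusions are not intended, correct Section 10.7.2 so that it claims only the exclusions that are listed.

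Either is a few lines in an amendment. The first may slow accrual slightly; the second would not, but it withdraws part of the stated protection. Neither needs a new test, visit or blood draw.

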## 10.8. Participant Study Drug Discontinuation Criteria

For all AEs/toxicity, the management and temporary/permanent discontinuation of the study drug should generally follow the criteria below, but clinicians should use their clinical judgment as to the best management for an individual participant.

- Grade 1 and Grade 2 AEs/toxicity:  
Continue the study drug. Manage using symptomatic measures and other concomitant medication, if appropriate.
- Grade 3 AEs/toxicity:  
Request laboratory results and repeat confirmatory laboratory results within 72 hours if relevant. Continue study drug pending receipt of the confirmatory laboratory tests/repeat observations, unless there is an immediate need to substitute ART. Continue to work-up to exclude other causes. Following confirmation of toxicity, and lack of other cause data (i.e., possibly, probably, or definitely related to the study drug) hold the treatment and follow abnormal laboratory values until they are Grade 2 or less.
- Grade 4 Potentially Life-Threatening or Fatal AEs/toxicity:  
Request laboratory results and repeat confirmatory laboratory results within 72 hours if relevant. Withhold the study drug at the discretion of the site investigator/ health care provider for clinical events, while awaiting a repeat assessment/ confirmation of an abnormal laboratory test. Continue to investigate to exclude other causes and make an assessment on relation to study drug or not. Following confirmation of toxicity and lack of other cause data: (i.e., possibly, probably, or definitely related to the study drug) the study drug should be discontinued immediately. Participants who permanently discontinue study treatment due to an adverse event related to the study treatment will continue to be followed in the study for safety monitoring at intervals to be determined by the investigator in consultation with the study team.

Study drug will be **permanently discontinued in participants** with the following condition:

- any grade 4 event on the DAIDS toxicity table
- a bilirubin at exchange value

In addition, study drugs will not be administered to any participant if the HIV NAT result comes back as positive at any time during the study.

## 10.9. Early Study Termination Criteria

The study can be terminated or suspended early by the Sponsor. Reasons for termination of the study may include, but are not limited to, the following:

- The investigator or study site exhibit serious and/or persistent non-adherence to the clinical study Protocol, the Declaration of Helsinki, ICH–GCP, and/or applicable regulatory requirements
- A DSMB recommendation to terminate the study

## 11. Study Safety and PK Exposures Criteria for Interim Analyses

### 11.1. Study Safety Hold Criteria

The following **safety hold criteria will lead to a pause/temporarily hold** in the study, until such time as the Serious Adverse Event Evaluation Group (Section 14.2) have reviewed the SAEs, determined causality, and informed the DSMB. The DSMB will assess causality and advise on study continuation or termination.

#### 11.1.1. Cohort 1A: Safety Hold Criteria

Accrual of neonates into Cohort 1A (n=8) will be paused if:

- 1 participant has a fatal or life-threatening adverse event assessed as related to study drug, or
- 2 participants experience the same related grade 3 or higher adverse event, or
- 3 participants experience different related grade 3 or higher adverse events

#### 11.1.2. Cohort 1B: Safety Hold Criteria

Accrual of neonates in Cohort 1B (n=8) will be paused if:

- 1 participant has a fatal or life-threatening adverse event assessed as related to study drug, or
- 2 participants experience the same related grade 3 or higher adverse event, or
- 3 participants experience different related grade 3 or higher adverse events

#### 11.1.3. Cohort 2: Safety Hold Criteria

Accrual of neonates in Cohort 2 (n=24) will be paused if:

- 1 participant has a fatal or life-threatening adverse event assessed as related to study drug, or
- 25% of participants (3 of the first 12; or 6 of 24 neonates) experience the same related grade 3 or higher adverse event, or
- Any related AE leading to permanent discontinuation of the study drug

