Creatinine will be graded according to the upper limits of 'normal' for a term neonate (**Table 9**), which will serve as a proxy for evaluating abnormal renal function. Study investigators will make use of protocol specific creatinine laboratory reference ranges (Appendix, **Table 18.1**) representing standardised accepted 'normal' creatinine levels for term neonates (45). At birth, creatinine values are elevated and reflect maternal renal function. Over the first 24 to 36 hours, a transient raise in creatinine levels occur, after which it falls quickly (day 5- 7 of life), and then creatinine levels stabilize at around 9 days (46). Given these renal physiological adaptations, a change from baseline creatinine and/ a change in creatinine clearance as per the DAIDS toxicity grading table will *not be used*, as these grading developed for children may be inaccurate in neonates.

A clinical grading system was developed for reporting hyperbilirubinemia making use of both clinical findings and intervention levels required to manage jaundice in the neonate (**Table 9**). Hyperbilirubinemia values will be captured and jaundiced will be managed according to the 2006 Western Cape Consensus Guidelines (Appendix, Section 18.2 (47)), as per standard of care. Neonates on phototherapy will be allowed to continue with study drug. Dolutegravir will be permanently discontinued in any neonate who requires an exchange transfusion.

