## 10.6. Hypersensitivity Reaction to Dolutegravir

Hypersensitivity reactions to DTG have been reported in less than 1% of participants in Phase 3 clinical trials and were characterized by rash, constitutional findings, and sometimes organ dysfunction, including liver injury. The DAIDS Toxicity Table will capture symptoms and signs of possible DTG hypersensitivity, and if suspected, will be managed as a SAE. Hypersensitivity to DTG is a multi-organ clinical syndrome usually characterized by fever, rash, general malaise, blisters or peeling of the skin, oral blisters or lesions, conjunctivitis, facial oedema, hepatitis, eosinophilia, angioedema, and difficulty in breathing. Clinical status, including liver aminotransferases, should be monitored and appropriate therapy initiated. Discontinue DTG as soon as a hypersensitivity reaction is suspected and if the diagnosis of DTG hypersensitivity is made DTG should never be re-started (17).

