While not a specific requirement for the selection of the multi-dose strategy the DTG  $AUC_{0-24}$  with the proposed dosing regimen will also be calculated and compared to the target of 35.1 to 134 (µg·h/mL) used in the IMPAACT 2019 study. This exposure range represents the lower 90% CI of the  $AUC_{0-24}$  observed in adults receiving 50 mg once daily and the upper 90% CI for observed in adults receiving 50 mg twice-daily.

### 11.5. Interim PK Analysis after Completion of 50% Enrolment in Cohort 2

An interim PK analysis is planned after 50% of participants have completed the follow-up in Cohort 2. The aim of a multi-dose strategy with paediatric solid formulations is to achieve DTG exposures comparable to those observed in adults and children, i.e., a DTG  $C_{24}$  above 0.67 µg/mL and a  $C_{max}$  below 17.0 µg/mL for the majority of neonates. The proportion of participants with an  $C_{24} < 0.5$  µg/mL ( $EC_{95}$ ) will also be calculated. The DSMB will review the interim PK data in relation to the observed  $C_{24}$  and  $C_{max}$  values and determine if a dose adjustment is required. A different DTG dosing schedule may be selected based on the data available for the remainder of Cohort 2 infants. Any change to the DTG dosing schedule will be agreed upon by the DSMB before implementation.

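### If the Cohort 2 schedule changes at the halfway review, the pooled same-event hold can need 4 to 6 of up to 12 new-schedule infants to pause accrual, against 3 of 12 before

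*Protocol*

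**What the plan says.** Protocol Section 11.1.3 lists three alternative triggers for pausing accrual into Cohort 2 (n=24). The first is one related fatal or life-threatening event. The second is the same-event limb: "25% of participants (3 of the first 12; or 6 of 24 neonates) experience the same related grade 3 or higher adverse event". The third is "Any related AE leading to permanent discontinuation of the study drug".

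Section 11.5, in line with Sections 6.1.2 and 9.2.3, plans an interim review once half the cohort has completed follow-up. It then states: "A different DTG dosing schedule may be selected based on the data available for the remainder of Cohort 2 infants". It adds: "Any change to the DTG dosing schedule will be agreed upon by the DSMB before implementation".

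Section 10.8 sets out how individual events are handled. For a confirmed related Grade 3 event the instruction is to "hold the treatment and follow abnormal laboratory values until they are Grade 2 or less". Permanent discontinuation is required for "any grade 4 event on the DAIDS toxicity table" and for bilirubin at exchange level. Section 10.4 says "Dolutegravir will be permanently discontinued in any neonate who requires an exchange transfusion", and exchange transfusion is Grade 3 bilirubin in Table 9. Section 10.6 says that "if the diagnosis of DTG hypersensitivity is made DTG should never be re-started".

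No section restarts the same-event count, or keeps it separately by schedule, when the schedule changes.

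**The concern.** The same-event limb is a 25% rule with an early look at 12 infants. That look protects whichever schedule Cohort 2 starts on. If the schedule changes at about that point, the second half receives a new exposure, but their events are added to a tally built on the old schedule and judged only against 6 of 24. A clean first half then becomes a reserve of allowed events for a schedule that did not earn it.

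This matters mainly if the change shortens the dosing interval. The candidate schedules in Table 4 run from every 72 hours to every 24 hours. Section 8.2.1 stresses the timing of the second dose, citing simulations in which giving it 24 rather than 48 hours after the first took Cmax above that study's target. The protocol also gives Cohorts 1A and 1B separate counts, although both receive the same single 5 mg dose.

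**Working it through.** **Inputs from the protocol.** Hold at 3 of the first 12 or 6 of 24 (11.1.3); review at 50%, so up to 12 infants remain (11.5). The stated threshold reproduces: 3/12 = 0.25 and 6/24 = 0.25.

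**Assumptions, not in the protocol.** The same-event rate p on the new schedule is 25% or 40%. The fraction f of those events that lead to permanent discontinuation, and so pause accrual after one case, runs from 0 to 1/3. All events are taken as the same adverse event, and all 12 remaining infants receive the new schedule.

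**Step 1: events still needed.** With x same events in the first 12, reaching 6 of 24 takes k = 6 − x.

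| x | k | k/12 |
|---|---|---|
| 0 | 6 | 50% |
| 1 | 5 | 42% |
| 2 | 4 | 33% |

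With x = 3 the limb has already fired once, and 3 more reach 6 of 24, so there is no gap.

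**Step 2: same-event limb alone (f = 0).** P(X ≥ k) for X ~ Bin(12, p):

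| p | k = 6 | k = 5 | k = 4 | fresh count, k = 3 |
|---|---|---|---|---|
| 0.25 | 0.054 | 0.158 | 0.351 | 0.609 |
| 0.40 | 0.335 | 0.562 | 0.775 | 0.917 |

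**Step 3: add the single-case discontinuation trigger.** The overall pause probability is

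1 − (1 − pf)^12 × BinomCDF(k − 1; 12, p(1 − f)/(1 − pf)).

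Worked case, p = 0.25, f = 0.2: pf = 0.05; (0.95)^12 = 0.540; conditional rate 0.20/0.95 = 0.2105. This gives the second row below.

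| p | f | x = 0 | x = 1 | x = 2 | fresh 3 of 12 |
|---|---|---|---|---|---|
| 0.25 | 0.1 | 0.290 | 0.351 | 0.478 | 0.666 |
| 0.25 | 0.2 | 0.473 | 0.507 | 0.586 | 0.718 |
| 0.25 | 1/3 | 0.652 | 0.666 | 0.704 | 0.781 |
| 0.40 | 0.1 | 0.553 | 0.687 | 0.827 | 0.930 |
| 0.40 | 0.2 | 0.709 | 0.783 | 0.870 | 0.943 |
| 0.40 | 1/3 | 0.844 | 0.874 | 0.916 | 0.958 |

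**Step 4: average over the first half.** If the original schedule has a 5% rate and 2 or fewer events were seen, the weights for x = 0, 1, 2 are 0.551, 0.348 and 0.101. At p = 0.25 and f = 0 the pause probability is 0.551 × 0.054 + 0.348 × 0.158 + 0.101 × 0.351 = 0.120, against 0.609. At f = 0.2 it is 0.496 against 0.718.

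**Step 5: extra pauses from a new-schedule trigger.** Let A and B be independent Bin(12, p), with the same rate in both halves. The current rule pauses if A ≥ 3 or A + B ≥ 6; the added trigger also pauses if B ≥ 3.

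| true rate | current | with added trigger |
|---|---|---|
| 2% | 0.0015 | 0.0031 |
| 5% | 0.0199 | 0.0388 |
| 10% | 0.1186 | 0.2094 |

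**The case against.** The strongest reply is that the gap is narrow and conditional. It needs an optional schedule change, no more than two earlier same events, and then repeated, identical, related Grade 3 events that do not end treatment. Bilirubin toxicity, the harm that most concerns this protocol, already pauses accrual after one related exchange transfusion. All of this stands and limits the weight of the point.

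The large figures also depend on f near 0. Section 10.8 says to hold the drug; it does not say that dosing resumes. Dosing ends by day 28 (9.2.3.4), so a hold may last until then. Whether that counts as permanent discontinuation is not stated. If it does, f rises and the gap shrinks: at f = 1/3 and a 25% rate it is 65% to 70% against 78%. This stands too. Rates of 25% to 40% are well above the 1% to 10% in Table 10; at 10%, a fresh 3-of-12 count would itself pause only 11% of the time with f = 0.

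The limb could be read as a running 25%, with the bracketed counts as examples. Two earlier events plus two among the first four new infants would then pause at 4/16. At a 25% rate and f = 0 this gives 6%, 20% and 47% for 0, 1 and 2 earlier events, still below 61%. The explicit counts favour the fixed reading, and the running reading does not close the gap.

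The count is also per cohort, and schedules may differ by birth weight from the outset, so the first 12 may already mix schedules. That is fair: this is a design choice, not a contradiction.

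Finally, there is oversight. Every Grade 3 event is an SAE, SAEs are reviewed monthly, and the DSMB must agree any change and meets at intervals set by accrual and SAEs. But that agreement precedes dosing on the new schedule, the monthly group is drawn from the study team, and none of these provisions sets a number. A condition might be set in the DSMB Charter, which is not at hand.

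**Conclusion.** The point holds as an optional, low-cost safety improvement. On the stated counts, a changed schedule loses the 3-of-12 check, and the same-event limb needs 6, 5 or 4 of up to 12 new-schedule infants after 0, 1 or 2 earlier events. At a 25% rate the chance of a pause falls short of a fresh count by 26 to 56 percentage points if every event is a temporary hold (61% against 35% down to 5%). With f = 1/3 the shortfall is about 8 to 13 points (78.1% against 70.4% down to 65.2%).

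The practical reach is related Grade 3 events such as isolated transaminase, creatinine or haematology abnormalities. The probabilities rest on assumed rates, an assumed f and 12 infants on the new schedule; the counts of 6, 5 and 4 do not depend on the rates or on f. Nothing is lost if the schedule stays the same.

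**What to change.** Add one sentence to Section 11.1.3, for example: *If the dosing schedule is changed, accrual is also paused once 3 infants on the new schedule, among up to the first 12 of them, have had the same related adverse event of Grade 3 or above.*

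Keep 6 of 24 alongside it. If 4 or 5 same events had already occurred and the schedule was then made less intense, the pooled count would need only 2 or 1 more, and replacing it with a fresh 3 would lose that sensitivity.

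The change needs no extra infants or staff and has no effect unless the schedule changes. It is a protocol modification needing approval before use (13.4), so it should be in place before the halfway review. If the schedule does change, the chance of at least one same-event pause over the whole cohort rises from 0.2% to 0.3% at a true 2% rate, from 2% to 4% at 5%, and from 12% to 21% at 10%. Each such pause is a temporary hold for review (11.1).
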